Higher care ward No YesIncreased nursing observations No YesAssigned a bed in view of nurses' station No YesFamily with patient in ward No YesSevere complications (tick all that apply): Superficial or deep surgical site, or body cavity infection N Y Postop day Bloodstream infection or ARDS N Y Postop day Pneumonia N Y Postop day Urinary tract or AKI N Y Postop day Postoperative bleed N Y Postop day Cardiac arrest N Y Postop day Other severe complication N Y Postop day Days in hospital after surgery Status at hospital discharge or 30th postoperative in-hospital day: Alive & still in hospital Dead Alive & discharged → if alive and discharged, was patient transferred to another facility for higher care? Yes NoIf deceased, photo of clinical note of death uploaded: Yes CRF completed and verified by..... on dd/mm/2019ASOS-2 unique patient ID

ASOS-2 Trial CRF v4 (Control arm)

Patient name: _____

DOB d m y y y Patient hospital number : _____ ASOS-2 unique patient ID

African Surgical OutcomeS-2 (ASOS-2) Trial: Case Record Form (CRF) (Intervention arm)

Age years (<30 points; 0 points/ 30-69 years; 1 point/ ≥70 years; 3 points) Sex M F

ASA I (0 points) II (2 points) III (5 points) IV (8 points) V (8 points)

Chronic co-morbid disease (tick all that apply): Hypertension HIV / AIDS Diabetes mellitus COPD / Asthma

Surgical procedure category (select single most appropriate): Gynaecology (minus 1 point) Obstetrics (minus 1 point)
 Orthopaedic (0 points) Ear, nose and throat (3 points) Plastics or breast (1 point) Urology (2 points)
 Neurosurgery (4 points) Gastro-intestinal or Hepato-biliary (3 points) Cardiothoracic/ vascular (3 points) Other (0 points)

Indication for surgery:
 Non-communicable disease (0 points) Caesarean section (minus 2 points) Trauma (1 point) Infection (2 points)

Urgency of surgery: Elective (0 points) Urgent (3 points) Emergency (4 points)

Severity of surgery: Minor (0 points) Intermediate (2 points) Major (4 points)

Start of surgery time (24h) & date: h h : m m d d m m 2 0 1 9

ASOS Surgical Risk Score points per risk factor:
 Age + ASA + Surgical procedure category + Indication for surgery + Urgency surgery + Severity surgery = points

Time that the ASOS Surgical Risk Score was calculated: Pre-op Intra-op Immediately post-op

Predicted ASOS Risk Score: Not high-risk patient (<10 points) High-risk patient (≥10 points)

Postoperative Follow Up

Not high-risk patient: (Indicate postoperative care given): Higher care ward No Yes Increased nursing observations No Yes
Assigned a bed in view of nurses' station No Yes Family with patient in ward No Yes

 High-risk patient: (Indicate all postop surveillance)	Day 0	Day 1	Day 2	Day 3	Day 4+
Higher care ward	 No  Yes				
Increased nursing observations	 No  Yes				
Assigned a bed in view of nurses' station	 No  Yes				
Family with patient in ward	 No  Yes				
'Postoperative surveillance bedside guide' at the patient's bedside?	 No  Yes				

Severe complications (tick all that apply): Superficial or deep surgical site, or body cavity infection N Y Postop day
Bloodstream infection or ARDS N Y Postop day Pneumonia N Y Postop day
Urinary tract or AKI N Y Postop day Postoperative bleed N Y Postop day
Cardiac arrest N Y Postop day Other severe complication N Y Postop day

Days in hospital after surgery

Status at hospital discharge or 30th postoperative in-hospital day: Alive & still in hospital Dead
 Alive & discharged → if alive and discharged, was patient transferred to another facility for higher care? Yes No
If deceased, photo of clinical note of death uploaded Yes CRF completed and verified by..... on dd/mm/2019

ASOS-2 unique patient ID ASOS-2 Trial CRF v4 (Intervention arm)

Patient name: _____ DOB d d m m y y y y

Patient hospital number : _____ ASOS-2 unique patient ID

Appendix 4

ASOS-2 Surgical Risk Calculator Score Card

The ASOS Surgical Risk Calculator Score card

The ASOS Surgical Risk Score is used to identify patients requiring 'increased postoperative surveillance'

How to calculate the ASOS Surgical Risk Score:

1. Calculate score before surgery using the table below
2. ASOS Surgical Risk Score = Age (points) + ASA (points) + Surgery timing (points) + Surgery severity (points) + Indication for surgery (points) + Surgery (points)
3. High-risk patients have ASOS Surgical Risk Score ≥ 10 points
4. A high-risk patient has an ASOS Surgical Risk Score ≥ 10 points
5. If ≥ 10 points, then organize 'increased postoperative surveillance' after surgery

Age	Points
18- 29	0
30-69	+1
≥ 70	+3
ASA	
ASA 1	0
ASA 2	+2
ASA 3	+5
ASA 4 and more	+8
Surgery timing	
Elective surgery	0
Urgent surgery	+3
Emergent surgery	+4
Surgery severity	
Minor	0
Intermediate	+2
Major	+4
Indication for surgery	
Non-communicable disease	0
Caesarean section	-2
Trauma	+1
Infection	+2
Surgery type	
Gynaecology/ obstetrics	-1
Plastics and breast	+1
Urology	+2
Ear, nose and throat, gastro-intestinal, hepato-biliary, cardiothoracic, vascular	+3
Neurosurgery	+4
All other types of surgery	0

Appendix 5

'Increased postoperative surveillance' bedside guide

'Increased postoperative surveillance' bedside guide

This is a 'high-risk' surgical patient

This patient requires 'increased postoperative surveillance' and is most likely to experience one of these complications postoperatively

'High-risk' patients most commonly experience the following complications.

Most common complications	Consider the following management
Cardiac arrest	Ensure staff know where the emergency drugs and defibrillator are stored
Surgical site infections	Swab wound for microbiology, and consider antibiotics
Bloodstream infections	Consider early blood cultures, and consider antibiotics
Pneumonia	Physiotherapy, mobilise early, sputum & blood cultures, & consider antibiotics
Acute kidney injury	Ensure adequate hydration, monitor the serum creatinine
Postoperative bleed	Look for signs of hypotension, and decreasing haemoglobin

**If for any reason you are concerned about the patient's condition postoperatively,
then please look for these complications**

Appendix 6

Statistical Analysis Plan

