6.3. Randomisation	12
6.4. Trial intervention	12
Intervention arm.....	12
Control arm	13
6.5. Data collection and collation	13
Dataset	13
6.6. Predefined protocol violation	14
6.7. Follow up procedures	14
6.8. Schedule of assessment	14
7. Statistical considerations	15
7.1. Sample size calculation	15
TABLE 1: Sample size calculations for the ASOS-2 Trial based on a power of 80%, 2-sided $\alpha = 0.05$ and a mean cluster size of 100 patients	15
7.2. Statistical analysis	16
7.3. Subgroup analyses	Error! Bookmark not defined.
7.4. Secondary studies	16
8. Research ethics	18

8.1 Ethical principles	18
9. Data handling and record keeping.....	19
10. Monitoring and auditing	20
10.1 Training of investigators	20
11. Trial management and committees.....	21
11.1 Trial management group.....	21
11.2 Trial Steering Committee	21
11.3 Data and Safety Monitoring Board	21
12. Data management and ownership	22
13. Publication plan and public communication of trial results	23
References	24
Appendix 1	25
African Surgical OutcomeS-2 (ASOS-2) Trial: Definitions document	25
Appendix 2	37
African Surgical OutcomeS-2 (ASOS-2) Trial: Hospital ‘broadcasting’ signage	37
Appendix 3	38
African Surgical OutcomeS-2 (ASOS-2) Trial: Case Record Form (CRF) (Control arm).....	38
African Surgical OutcomeS-2 (ASOS-2) Trial: Case Record Form (CRF) (Intervention arm).....	39
Appendix 4	40
ASOS-2 Surgical Risk Calculator Score Card	40
Appendix 5	41
‘Increased postoperative surveillance’ bedside guide.....	41

1. List of abbreviations

ASOS	African Surgical Outcomes Study
EuSOS	European Surgical Outcomes Study
ISOS	International Surgical Outcomes Study

2. Summary

Short title	ASOS-2 Trial
Methodology	An international, multicentre, African cluster randomised trial
Research sites	Hospitals undertaking adult surgery in participating countries.
Objectives	To determine whether increased postoperative surveillance in high-risk adult surgical patients reduces overall in-hospital mortality in surgical patients aged 18 years and over in Africa.
Number of patients	664 hospital clusters with a recruitment target of 100 patients per site (approximately 66,400 patients)
Inclusion criteria	All consecutive adult patients aged 18 years and over admitted to participating centres undergoing elective and non-elective surgery

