7.1. Sample size calculation

This is a cluster randomised trial of hospitals in Africa. We will match hospitals on expected surgical volume in a week of surgery. This varied tremendously across the ASOS group; with a median number of surgical procedures per hospital for the study week in ASOS of 29 (IQR 10-71).⁸ The variability of the individual patient outcomes explained by the cluster (or surgical site) is taken into account in these sample size calculations. The intra-cluster correlation coefficient (ICC) in ASOS was 0.01. For the sample size calculation, we have therefore used a conservative ICC of 0.015.

Based on ASOS, we estimate the coefficient of variance for a 4-week recruitment period to be 0.63. A 4-week recruitment period is defined as the following; i) hospitals stop recruiting at the end of the week in which they have exceeded 100 enrolled patients, and ii) if a site had not reached 100 enrolled patients after 4 weeks of recruiting, it would stop recruiting.

The incidence of mortality in ASOS was 2.1%.⁸ We expect a 25% relative risk reduction in mortality through increased surveillance of postoperative surgical patients at high-risk of severe complications or in-hospital mortality. Based on the intra-cluster correlation coefficient (ICC) for the composite of severe complications and mortality in ASOS-2 of 1.5%, a coefficient of variance of 0.63, and stratification for the level of the surgical facility, and the volume of procedures per week, a trial for efficacy of increased postoperative surveillance would require 64,200 patients, from 642 surgical centres across Africa (Table 1).⁸ Based on a relative risk reduction of 25% in the intervention arm, the sample sizes for the primary outcome are shown in Table 1.

TABLE 1: Sample size calculations for the ASOS-2 Trial based on a power of 80%, 2-sided $\alpha = 0.05$ and a mean cluster size of 100 patients

Primary outcome (in-hospital all-cause mortality)					
Control event rate	Intervention arm	Relative risk	Intra-cluster correlation coefficient (ICC)	Coefficient of variance (CV)	Total clusters
2.0%	1.5%	0.75	0.015	0	536
2.0%	1.5%	0.75	0.015	0.63	664
2.0%	1.6%	0.80	0.015	0.63	1068

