During the trial an external auditor ([name]) will check the event rate in the control arm of the study once 80% of all recruited patients have been captured on REDCap (practically this will take place around September 2019). The external auditor will use the event rate in the control arm to decide whether recruitment should continue beyond the target of 664 hospitals, and for how many months recruitment should continue. This specified interim analysis of data will not lead to adjustment of the prespecified alpha of 0.05.

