2. The infection appears to be related to the surgical procedure and involves deep soft tissues of the incision (e.g. fascial and muscle layers) and
3. The patient has at least one of the following:

- a. purulent drainage from the deep incision but not from the organ/space component of the surgical site
- b. a deep incision spontaneously dehisces or is deliberately opened by a surgeon and is culture-positive or no cultures were taken whilst the patient has at least one of the following signs or symptoms of infection: fever ($>38^{\circ}\text{C}$) or localized pain or tenderness. A culture-negative finding does not meet this criterion.
- c. an abscess or other evidence of infection involving the deep incision is found on direct examination, during surgery, or by histopathologic or radiologic examination
- d. diagnosis of a deep incisional surgical site infection by a surgeon or attending physician

Surgical site infection (organ/space)

An infection which involves any part of the body excluding the fascia or muscle layers and meets the following criteria:

1. Infection occurs within 30 days after surgery and
2. The infection appears to be related to the surgical procedure and involves any part of the body, excluding the skin incision, fascia, or muscle layers, that is opened or manipulated during the operative procedure and
3. The patient has at least one of the following:
 - a. purulent drainage from a drain that is placed through a stab wound into the organ/space
 - b. organisms isolated from an aseptically obtained culture of fluid or tissue in the organ/ space
 - c. an abscess or other evidence of infection involving the organ/space that is found on direct examination, during reoperation, or by histopathologic or radiologic examination
 - d. diagnosis of an organ/space surgical site infection by a surgeon or attending physician

Bloodstream infection

An infection which is not related to infection at another site and which meets at least one of the following criteria:

1. Patient has a recognised pathogen cultured from blood cultures which is not related to an infection at another site

2. Patient has at least one of the following signs or symptoms: fever ($>38^{\circ}\text{C}$), chills, or hypotension and at least one of the following:
 - a. common skin contaminant cultured from two or more blood cultures drawn on separate occasions

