2. TRIAL OUTCOME EVENTS

2.1. Primary effectiveness outcome for evaluation of increased postoperative surveillance for high-risk patients:

In-hospital death censored at 30 days if the patient is still alive and in-hospital.

2.2. Secondary effectiveness outcome:

Composite of severe in-hospital complications and death censored at 30 days if the patient is still alive and in-hospital.

Severe complications are:

- I. Superficial or deep surgical site, or body cavity infection
- II. Bloodstream infection or ARDS
- III. Urinary tract or AKI
- IV. Cardiac arrest
- V. Pneumonia
- VI. Postoperative bleed
- VII. Other severe complications

The definitions of all the secondary outcomes are given in the Appendix 1: Definitions document.

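### A bedside guide used only at intervention sites can raise detection of secondary-composite complications in that arm, and the SAP plans no analysis that would show it

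*Combined protocol and SAP*

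**What the plan says.** **The prompt.** Protocol 6.4 has the guide displayed at the bedside of every patient flagged as high-risk in the intervention arm; control sites give usual care. The guide (Appendix 5) names six complications, each with actions that staff are asked to consider. For surgical site infection the entry is "Swab wound for microbiology, and consider antibiotics". For acute kidney injury (AKI) it is "Ensure adequate hydration, monitor the serum creatinine". For bloodstream infection it suggests early blood cultures. It closes by asking staff who are worried about a patient to look for the listed complications.

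**The outcome.** SAP 2.2 defines the secondary outcome as "Composite of severe in-hospital complications and death censored at 30 days if the patient is still alive and in-hospital". It is counted in all adult surgical patients, has seven complication items, and uses the same model as the primary outcome (SAP 3.2.1). Every complication on the guide is also in the composite.

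**The definitions.** In protocol Appendix 1, one route to bloodstream infection is "Patient has a recognised pathogen cultured from blood cultures which is not related to an infection at another site". The other needs a clinical sign plus a positive culture or antigen test. A complication is severe only if it clearly lengthens the stay, leaves lasting functional loss or ends in death. The definitions are offered as guidance for uncertain cases.

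**Recording.** A site investigator takes outcomes from the medical records (protocol 6.7), on a case record form (CRF) that is specific to the arm (Appendix 3). Deaths call for a photo of the clinical note; complications have no equivalent. SAP 3.2.2 plans a sensitivity analysis for unobserved outcomes only.

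**The concern.** The intervention is surveillance, and part of it asks staff to test for, and look for, the events that the secondary outcome counts. If one arm looks harder, its recorded rate can rise with no change in the true rate. A neutral or unfavourable composite could then mean that the intervention failed, or that it worked partly by finding more cases.

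The plan as written offers no means of telling these apart. The text provided describes no blinded assessment, no adjudication and no common testing schedule. The outcome section of the CRF does not record how many tests were done, so a difference in testing could not be measured from it afterwards. SAP 3.2.3 closes the list of pre-specified analyses, so any later check would be post hoc.

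**Working it through.** **Step 1. Guide against definitions (Appendix 5 against Appendix 1).**

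| Item | Action on the guide | Role of that action in the definition | Link |
|---|---|---|---|
| Bloodstream infection | Early blood cultures | Positive culture or antigen test required | Close |
| AKI | Monitor creatinine | One route; renal replacement and urine output are others | Close for that route |
| Surgical site infection | Wound swab | One route; pus or a clinician's diagnosis also suffice. A negative culture rules out some criteria | Partial, in both directions |
| Pneumonia | Sputum and blood cultures | None; radiograph plus clinical findings | Not through culture |
| Postoperative bleed | Falling haemoglobin, hypotension | None; blood loss that would normally be transfused | Indirect only |
| Cardiac arrest | Location of emergency equipment | None; a clinical event | None through testing |
| Urinary tract infection | Not on the guide | Urine culture required | None |

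So three items have a direct link to the guide's tests, and two of those links are close.

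**Step 2. Reproduce the plan's own figure.** Inputs from protocol 7.1, Table 1: mean cluster size 100, intra-cluster correlation (ICC) 0.015, coefficient of variation (CV) 0.63, 80% power, two-sided 0.05. The row is "2.0% 1.5% 0.75 0.015 0.63 664".
- Design effect = 1 + ((0.63² + 1) × 100 − 1) × 0.015 = 1 + 138.69 × 0.015 = 3.08.
- Patients per arm without clustering, 2.0% against 1.5%, pooled variance, no continuity correction: 10,795.
- Clusters = 2 × 10,795 × 3.08035 / 100 = 665.0, against the stated 664.

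The design effect therefore matches the plan. Protocol 7.1 also attributes the ICC of 1.5% to the composite, so the same design effect is used below with 33,200 patients per arm (664 × 100 / 2).

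**Step 3. Form of the bias.** Observed RR = true RR × (1 + f × k). Here f is the share of composite events that are test-dependent and occur in high-risk patients, and k is the relative rise in detection in the intervention arm. The documents give neither value, nor a composite event rate p. All three are assumptions.

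**Step 4. No true effect.** SE(log RR) = √[2 × 3.08 × (1 − p) / (33,200 × p)]. The limit of significance for harm is exp(1.96 × SE), and the rise in detection that brings the expected RR to it is k = (limit − 1) / f.

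| Assumed p | SE | RR limit | k at f = 0.25 | k at f = 0.5 | k at f = 0.75 |
|---|---|---|---|---|---|
| 5% | 0.059 | 1.12 | 49% | 25% | 16% |
| 10% | 0.041 | 1.08 | 33% | 17% | 11% |
| 15% | 0.032 | 1.07 | 26% | 13% | 9% |

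At the limit the chance of a significant result is about one half. A separate power calculation at the effective size (33,200 / 3.080 = 10,778 per arm) agrees. With f = 0.5 and k = 20% the expected RR is 1.10, and the chance of a significant result is 38%, 67% and 86% at p = 5%, 10% and 15%.

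**Step 5. A true benefit.** The rise in detection that cancels it is k = (1 / true RR − 1) / f.
- True RR 0.90: 44%, 22% and 15% at f = 0.25, 0.5 and 0.75.
- True RR 0.75: 133%, 67% and 44%.

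With true RR 0.90, f = 0.5 and k = 20%, the observed RR is 0.90 × 1.10 = 0.99. The chance of a significant result falls from 41% to 4% at p = 5%, and from 88% to 5% at p = 15%.

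**The case against.** The other side has real force on five points.

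- **The links are fewer than they look.** A reader might infer that haemoglobin checks, sputum cultures and urine cultures prompted by the guide define composite items. They do not: the bleed item has no haemoglobin criterion, pneumonia has no culture criterion, and the guide does not mention urine. This stands.
- **The guide is worded softly.** Its actions are for consideration, it sets no testing schedule, and its closing line depends on concern about the patient. This stands, but control sites receive no prompt at all.
- **The severity requirement filters out trivial findings.** It does, in part. It is applied locally under definitions given as guidance, and treatment after a positive test can itself lengthen the stay.
- **The share affected may be small.** Only high-risk patients get the guide, while the composite is counted in everyone, and a patient with several complications counts once. This stands, and it is why f is shown down to 0.25.
- **The direction is not certain.** A reader might infer that the bias can only run against the intervention. Negative cultures can remove wound infections from the count, and recording by staff who know the arm could favour either side. Against the intervention is the likelier direction, not the only one.

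The CRF captures each complication item in both arms, so component tables could be made without any change. The SAP does not commit to them.

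**Conclusion.** The concern holds in a limited form. Detection of bloodstream infection, of AKI by creatinine and, less directly, of surgical site infection can differ by arm because of the intervention's own content. Nothing in the text provided prevents this or would reveal it.

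Its size cannot be derived from the documents. The figures are illustrations that rest on assumed values of f, k and the composite rate, and on the planned 664 clusters of 100. They show that a modest difference in detection (about 13% to 25% if half of events are affected) could produce an apparent harm, and that about 22% could hide a true RR of 0.90.

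Two stronger readings are not supported. One is that a benefit of the size planned for mortality (RR 0.75) would be wiped out; that needs about 67% more detection at f = 0.5, and the documents give no reason to expect so much. The other is that the trial's main conclusion is at risk; the primary outcome is death and does not depend on these tests. The point concerns how the secondary outcome is interpreted, and the remedy is a cheap improvement.

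**What to change.** Keep the composite as the secondary outcome and add to SAP 3.2.1:

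1. A pre-specified supportive analysis of death or cardiac arrest under the same generalised estimating equation model. These outcomes depend least on the tests that the guide prompts. Cardiac arrest is not wholly free of detection effects, since it is on the guide and a bed in view of the nurses may affect its recognition. Postoperative bleed also needs no laboratory value, but the guide's haemoglobin and hypotension prompts could affect its recognition.
2. Each of the seven CRF complication items by arm, with RR and 95% confidence interval. State that the paired items (bloodstream infection with ARDS, urinary tract infection with AKI) cannot be separated, so prompted and unprompted events stay mixed within them.
3. A statement that the composite will be interpreted alongside items 1 and 2, naming differential detection as a possible explanation of a neutral or unfavourable result. There should be no rule that item 1 must agree before benefit or harm is concluded. The direction of a rarer endpoint should not veto the composite, least of all an observed benefit when the likelier bias runs against the intervention.

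The cost is a few lines of SAP text, one extra model and one table, all from data already on the CRF. The drawback is that the supportive endpoint has fewer events, a wider interval and a heavy overlap with the primary outcome.
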